- Upper extremity weakness defined as a score of >11 and ≤56 on the arm motor Fugl-Mayer motor scale.
- Minimal pre-stroke disability defined as a score of <3 in the Modified Rankin Scale.
- Subjects need to be able to follow directions and participate in 2 hours of testing with short breaks.
- Subjects need to be able to provide informed consent.

[figure not shown]
Exclusion Criteria:

- Any substantial decrease in alertness, language reception, or attention that might interfere with understanding instruction for motor testing
- Excessive pain in any joint of the paretic extremity (not applicable to severe stroke subjects), as self reported
- Contraindications to single pulse TMS (will be used to measure cortical excitability) such as: history of seizures, unexplained loss of consciousness, any metal implants in the head, frequent or severe headaches or neck pain, any other electronic implanted medical devices such as pacemakers, defibrillators, or implant medication pump.

- Patients who are currently taking fluoxetine should accept a 5 week washout period before baseline (to be reconfirmed during baseline visit).
- Patients taking any other SSRI at the time of enrollment or in the previous month (the patients should accept a 5 week washout period before baseline to be reconfirmed during baseline visit).
- Patients taking any other medication likely to have adverse interaction with SSRIs (all the medications the patient is taking will be carefully reviewed, as noted below in "Monitoring of important drug interactions").
- Active depression on admission to SRH defined by a score of 24 or higher in the Hamilton Depression Rating Scale (HAM-D)
- Concurrent medical condition likely to worsen patient's functional status in the next 6 months such as: cancer, terminal heart, kidney or liver disease, as self-reported and/or confirmed by medical record.
- Pregnancy.

VII. STUDY OVERVIEW AND PROCEDURES

Study overview:

This study is a parallel, randomized, double blind, placebo controlled clinical trial. We will use the same duration and regimen of fluoxetine treatment as the FLAME trial as this trial showed that fluoxetine is efficacious when compared against placebo. Subjects will be randomized to one of three groups, where they will receive: 1) fluoxetine + active rTMS, 2) fluoxetine + sham rTMS or 3) sham rTMS + placebo fluoxetine. With a total of 45 patients, 15 patients will be randomized to each group using a computer based randomization program.

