This study is structured in 3 visits where baseline and post intervention assessments will be collected, 10 daily stimulation sessions (from 3^{rd} until 12^{th} visit), and subsequently, subjects will return for a weekly stimulation session for the next 8 weeks (visit 14^{th} to 21^{th}). Last visit will be the 22^{nd} and the whole battery of assessments is going to be collected. A table of the study flow is presented below.

Protocol Details:

There will be ten stimulation visits (to be given over a period of 15 days), followed by weekly sessions of stimulation for the next 8 weeks. During each stimulation visit, rTMS equipment will be placed on the subject's unaffected hemisphere over the primary motor cortex (M1). They will receive either active or sham rTMS with fluoxetine – or sham rTMS and placebo. The 30 subjects randomized to receive sham rTMS will have the opportunity to enroll into an open label at the conclusion of their participation in the randomized portion of the trial. This will consist of 10 daily active stimulation sessions that can be carried out over the course of 2 weeks. Subjects will only receive rTMS and not the study drug, Fluoxetine.

Intervention Details:

Repetitive transcranial magnetic stimulation:

Low frequency rTMS stimulation (active stimulation)

• During this stimulation session, the participant will receive a session of low-frequency rTMS to the primary motor cortex of the unaffected cerebral hemisphere. The resting motor threshold (MT) of the first dorsal interosseous (FDI) in the affected and unaffected hemispheres will be measured. The participants will receive the rTMS over the area corresponding to the "hot spot" for stimulation as defined by motor threshold determination, as described by prior rTMS application studies (Rossini et al., 1994).

• Low frequency rTMS stimulation will be applied according to the following parameter: intensity of 100% MT, frequency of 1 Hz, 1200 pulses as a single, continuous train lasting 20 minutes. This intervention is associated with significant motor gains in chronic (Mansur, 2005)(Fregni, 2006) and acute stroke. In addition, it is a safer approach to be used in chronic stroke (Fregni review).

Sham rTMS stimulation:

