For the first aim, the primary outcome will be motor function changes as indexed by Jebsen Taylor Hand Function test and secondary outcome will be Fugl-Meyer motor scores. Differences between the two groups will be tested using Student's t-test and, in addition, we will adjust for important baseline variables and also test the time effect in general mixed longitudinal models. Secondary analyses will be conducted in an exploratory manner (no correction for multiple comparisons). [We will also conduct exploratory correlational analysis as to understand whether beneficial effects of the combined intervention (active rTMS and fluoxetine) are associated with any baseline characteristics as to explore potential predictors of the effects of treatment. This result may also be used along with results for aim 2 to understand the mechanisms of the combined treatment.]

[For subaim 1: the primary outcome will be motor function changes as indexed by Jebsen Taylor Hand Function test and secondary outcome will be Fugl-Meyer motor scores. We will conduct the same analysis as aim 1 (Differences between the two groups will be tested using Student's t-test with adjustment for covariates) but in this case we conduct two comparisons (real rTMS+fluoxetine vs. sham rTMS+placebo fluoxetine and sham rTMS+fluoxetine vs. sham rtMS+placebo fluoxetine)]

For the second aim, we will initially build a mixed ANOVA model in which the dependent variable will be the parameters of cortical excitability and plasticity (PAS) indexed by

neuropsychological measures. The independent variables will be group [(active and placebo control)], time and the interaction group/time. [If we find a significant interaction effect between group and time, we will confirm our hypothesis that TMS induces a significant differential plasticity when compared to fluoxetine alone. Furthermore we will conduct additional analysis in which we will change the groups in the variable group (real rTMS+fluoxetine vs. sham rTMS+placebo fluoxetine and sham rTMS+fluoxetine vs. sham rtMS+placebo fluoxetine)

	·

Adeyemo, B. O., Simis, M., Macea, D., & Fregni, F. Systematic Review of Parameters of Stimulation: Clinical Trial Design Characteristics and Motor Outcomes in Noninvasive Brain Stimulation in Stroke. *Frontiers in Psychiatry*, *3*, 8.

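### On its most natural reading Aim 1 is decided by an unadjusted t-test on Jebsen Taylor change; an ANCOVA on the baseline score already collected would cost almost nothing and can gain precision

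*Combined protocol and SAP*

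**What the plan says.** The statistical text for the first aim makes change in the Jebsen Taylor test the primary outcome and Fugl-Meyer the secondary one. The group comparison is then described as follows: "Differences between the two groups will be tested using Student's t-test and, in addition, we will adjust for important baseline variables". The sentence continues with a third analysis: "and also test the time effect in general mixed longitudinal models". No covariate is listed, and none of the three analyses is named as the one that decides the aim.

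The next paragraph, for subaim 1, says "We will conduct the same analysis as aim 1" and spells that out as "Differences between the two groups will be tested using Student's t-test with adjustment for covariates". Here the adjustment is part of the test; in the Aim 1 paragraph it is an addition to it.

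On size and data, Section VII (Study overview) states that "15 patients will be randomized to each group using a computer based randomization program", so Aim 1 compares 15 with 15. It also says "This study is structured in 3 visits where baseline and post intervention assessments will be collected" and schedules the full battery at the last visit. A baseline and a final Jebsen Taylor score are therefore already planned for every patient.

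**The concern.** The wording of the Aim 1 paragraph puts the t-test first and the adjustment second, so a reader would take the unadjusted t-test on change as the deciding test. A change score subtracts the whole baseline value, which amounts to assuming that final score rises one-for-one with baseline. If the true slope is lower, the subtraction adds noise that a fitted slope would remove.

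Entry criteria are broad (arm Fugl-Meyer above 11 up to 56, stroke up to two years earlier), so baseline hand function is plausibly prognostic. With 15 patients per arm, lost precision is hard to recover elsewhere. What is at stake is power and interval width for the main comparison, not the validity of the test.

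**Working it through.** **The plan's own figure.** 3 arms × 15 = 45, which agrees with the stated total. Nothing further can be reproduced: the text gives no alpha, power, effect size, SD or dropout rate.

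**Inputs.** From the documents: 15 v 15, outcome is change, baseline score available. Assumed: two-sided 5%, complete normal data, true difference 0.8 final-score SD. The correlation ρ between baseline and final score, and the ratio k = final SD / baseline SD, are also assumed and are varied.

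**Formulas**, in units of the final-score SD:

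- t-test on change: V_c = (1 + k² − 2ρk)/k², SE = √(V_c × 2/15), 28 df, critical t 2.048.
- ANCOVA: V_a = (1 − ρ²) × 27/26, SE = √(V_a × 2/15), 27 df, critical t 2.052. The factor 27/26 = 1.038 is the price of estimating the slope.

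Leaving that factor aside, the ratio of ANCOVA to change-score variance is k²(1 − ρ²)/(1 + k² − 2ρk). Denominator minus numerator is (1 − ρk)², so the gain is zero when the slope ρk equals 1 and grows with the slope's distance from 1.

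**Worked case, k = 1, ρ = 0.5.**

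- Change: V_c = 2 − 2(0.5) = 1; SE = √0.1333 = 0.365; noncentrality 0.8/0.365 = 2.19; power 56%.
- ANCOVA: V_a = 0.75 × 1.038 = 0.779; SE = √(0.779 × 0.1333) = 0.322; noncentrality 0.8/0.322 = 2.48; power 67%.

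**Power (%), t-test on change v ANCOVA, from the noncentral t:**

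| ρ | k = 0.7 | k = 1 | k = 1.3 |
|---|---|---|---|
| 0.3 | 30 v 58 | 43 v 58 | 51 v 58 |
| 0.5 | 39 v 67 | 56 v 67 | 64 v 67 |
| 0.7 | 54 v 83 | 78 v 83 | 84 v 83 |
| 0.8 | 68 v 93 | 92 v 93 | 94 v 93 |
| 0.9 | 87 v 99.7 | 99.7 v 99.7 | 99.6 v 99.7 |

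At k = 1 the variances break even where (1 + ρ)/2 × 27/26 = 1, that is ρ = 52/27 − 1 = 0.93.

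**Worst case for ANCOVA.** With the slope exactly 1 the two variances differ only by 27/26. Over all effect sizes the largest loss is about 1.8 points, from about 67% to 65.5%.

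**Sensitivity, k = 1, same five correlations.**

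- 12 completers per arm: 35 v 48, 47 v 56, 68 v 72, 84 v 86, 98.7 v 98.7%.
- Skewed (lognormal) data, simulated: 48 v 65, 61 v 72, 79 v 85, 91 v 93, 98.6 v 99.2%.

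**Why one covariate.** At 15 v 15 a single useless covariate widens the confidence interval by about 2%; three widen it by about 7%, five by about 12% and eight by about 21%. An open list is not free.

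**The case against.** The strongest reply is that adjustment is already planned. The subaim paragraph equates its covariate-adjusted test with the Aim 1 analysis. If that adjusted analysis leads and baseline Jebsen Taylor is among its covariates, nothing is lost and only a wording gap remains. This stands as a limit: the power figures price one reading, the likelier one, and the text does not settle which is meant. For the same reason a reader should not infer that the plan omits baseline adjustment.

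It is also fair that the gain rests wholly on assumed ρ and k. The largest contrasts need a final SD well below the baseline SD, and at k = 1.3 with ρ of 0.7 or 0.8 ANCOVA is about a point worse. The table shows that precision can be gained, not that this trial loses any.

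Three stronger readings are tempting, and the documents support none of them:

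- **Inflated type I error.** This would follow only if success could be claimed on either the unadjusted or the adjusted result. The plan states no such rule. The sentence "Secondary analyses will be conducted in an exploratory manner (no correction for multiple comparisons" concerns secondary analyses and does not create one.
- **Chance baseline imbalance as a further harm.** Imbalance is already in the standard error of the t-test on change, so counting it separately counts the same precision loss twice.
- **No stratification.** The public text is visibly cut where randomisation details would sit, so its absence cannot be asserted.

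**Conclusion.** The point holds as an inexpensive improvement to the deciding analysis. The t-test on change is valid; it is simply a less efficient choice over much of the plausible range. With equal baseline and final SDs the gain is about 15 power points at ρ = 0.3, 11 at 0.5, 5 at 0.7, 1 to 2 at 0.8 and none at 0.9. It is larger if the final SD is below the baseline SD, and nil or about one point negative when the slope is near or a little above 1. It is zero if the sponsor already intends baseline-adjusted analysis to lead.

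All of this assumes a two-sided 5% test, 15 v 15, a difference of 0.8 final-score SD and a roughly linear relation between baseline and final score. Bunching of scores from subtasks that patients cannot complete is not in these figures. That affects the exact power values, not the mismatch between the Aim 1 and subaim paragraphs.

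**What to change.** State one deciding analysis for Aim 1: an ANCOVA of the final-visit (three-month) Jebsen Taylor score on treatment group, with baseline Jebsen Taylor score as the pre-named covariate, estimating active rTMS plus fluoxetine minus sham rTMS plus fluoxetine. Use the same model for both subaim comparisons against sham plus placebo, so that the two paragraphs agree. Label the unadjusted t-test, any analysis with further covariates and the longitudinal mixed model as supportive.

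While editing, name the treatment contrast of the Aim 1 mixed model. Only a time effect is mentioned there, whereas the Aim 2 model lists group along with "time and the interaction group/time".

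The cost is a few sentences and one degree of freedom, at most about 1.8 power points. No visit, measurement or change in sample size is needed.

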[figure not shown]
[figure not shown]
ORGANIZATION OF DETAILED PROTOCOL

Title: Effects of contralesional repetitive magnetic stimulation combined with fluoxetine on motor recovery in stroke patients
Protocol #:2014P001046
Date: 08/10/2017

[figure not shown]

Aim 1: Determine whether low-frequency rTMS of the unaffected M1 associated with fluoxetine offers an additional benefit on motor function over pharmacotherapy (fluoxetine) alone after three months of the combined therapy. Our hypothesis is that low-frequency rTMS combined with fluoxetine will induce greater improvement in motor function as compared to sham rTMS and fluoxetine.

Sub Aim 1.1: As to control for the effects of spontaneous recovery, we will also assess whether the superior effects of the combined effects will be superior to spontaneous recovery by comparing the results of the two groups against a placebo group (placebo fluoxetine and sham rTMS). We hypothesize that both groups (combined treatment and fluoxetine alone) will have a superior effect as compared to placebo only.

Aim 2: Determine whether fluoxetine combined with rTMS results in additional positive modulation of motor cortex excitability and cortical plasticity as compared to fluoxetine alone. Our hypothesis is that active rTMS combined with fluoxetine will induce a greater increase in the amplitude of motor evoked potential and greater LTP-like (long-term potentiation) as indexed by PAS-25 of the affected hemisphere (M1) as compared to sham rTMS combined with fluoxetine.

V. SUBJECT SELECTION

We will recruit 45 patients with ischemic stroke. The desired sample size is calculated, with some assumptions, based on the amount of patients treated in Spaulding Rehabilitation Hospital and affiliate hospitals and clinics. The study eligibility criteria that will be used for this study are based on the FLAME trial (as we will investigate the additional benefits of combining fluoxetine with rTMS). We broadened the motor score criteria and time since stroke in order to significantly improve the impact of the study and improve our understanding of the mechanisms behind plasticity after stroke in a broad population.

Subjects will conform to the following criteria:

Inclusion Criteria:

- Ischemic infarction within the past 2 years post event that has caused hemiparesis or hemiplegia, as self-reported and/or confirmed by medical record.
- Older than 18 years old.

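### Aim 1 leads with a t-test on Jebsen Taylor change that, unless values are imputed, omits randomised patients without a visit 22 score; the mixed model carries no group contrast at three months

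*Combined protocol and SAP*

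**What the plan says.** Aim 1 asks whether rTMS plus fluoxetine adds benefit "over pharmacotherapy (fluoxetine) alone after three months of the combined therapy". The statistical text for the first aim states that "the primary outcome will be motor function changes as indexed by Jebsen Taylor Hand Function test". It then says "Differences between the two groups will be tested using" Student's t-test, with adjustment for baseline variables placed after it as an addition. The same sentence continues that the investigators will "also test the time effect in general mixed longitudinal models". The paragraph on the sub-aim applies the same analysis to two further comparisons, each fluoxetine arm against double placebo.

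On timing, Section VII (Study overview) says: "This study is structured in 3 visits where baseline and post intervention assessments will be collected". Daily stimulation occupies visits 3 to 12, after which "subjects will return for a weekly stimulation session for the next 8 weeks" (visits 14 to 21). Visit 22 is the last, "and the whole battery of assessments is going to be collected". The study flow table is not in the available text. Allocation is 15 patients to each of three arms, 45 in total.

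The available text gives no analysis population, no imputation rule or other missing-data method, and no expected dropout.

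**The concern.** A t-test on change to visit 22 needs both a baseline and a visit 22 value. A patient who leaves after the daily sessions has no change score at three months. Without imputation, that patient is absent from the test that leads Aim 1, despite having been randomised and perhaps having an intermediate score. The model that could retain such a patient has the stated job of examining time, not of estimating the group difference at three months.

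Loss is plausible: the course runs to 22 visits with 90 days of daily pills. It could differ by arm, because stimulation and drug each bring their own side effects, which the plan tracks. If those who leave one arm are mainly those with little early gain, the t-test compares the patients who stayed rather than the groups as randomised. With 15 per arm, 10% dropout is 1.5 patients and 20% is 3. It is also unclear which result decides Aim 1 if the t-test, the adjusted analysis and the mixed model disagree.

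**Working it through.** **1. The plan's own figures.** 3 × 15 = 45, and 2 × 15 = 30 sham patients; both agree with the text. No effect size, SD, alpha, power or dropout is given, so the sample size cannot be reproduced from a power formula. Assuming two-sided 5% and 80% power, the detectable standardised difference from the two-sample t-test (noncentrality d√(n/2), 2n − 2 degrees of freedom) is 1.06 with 15 per arm, 1.15 with 13, 1.20 with 12 and 1.33 with 10.

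**2. When the completers' t-test is biased.** Let C be the change from baseline to visit 22, signed so that positive is improvement. The t-test estimates E(C | observed, active) − E(C | observed, control). With no true effect this is zero if the two selection terms are equal, whatever their size. Under the null, then, bias needs dropout that is both related to outcome and different between arms.

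**3. Assumptions for size (none is in the documents).** 15 per arm; normal scores with SD 1 at baseline, mid-study and final; correlations (baseline–mid, mid–final, baseline–final) of 0.80/0.85/0.75 (set A) or 0.70/0.80/0.65 (set B); 10% or 20% dropout after the mid assessment; log-odds of dropout −1.5 per SD of early change; 5,000 simulated trials per scenario. SD of change = √(2(1 − ρ)) with ρ the baseline–final correlation: √0.50 = 0.707 for A and √0.70 = 0.837 for B.

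**4. Selective dropout in the active arm only, no true effect.**

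| Set, dropout | t-test bias (baseline SD) | Divided by SD of change |
|---|---|---|
| A, 10% | 0.055 | 0.055/0.707 = 0.08 |
| A, 20% | 0.114 | 0.114/0.707 = 0.16 |
| B, 10% | 0.073 | 0.073/0.837 = 0.09 |
| B, 20% | 0.131 | 0.131/0.837 = 0.16 |

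The t-test's type I error is 5.6% to 7.0% (Monte Carlo SE √(0.05 × 0.95/5000) = 0.3 points). Adjusting completers for baseline still leaves a bias of 0.05 to 0.10. The likelihood-based repeated-measures estimate is biased by at most 0.005.

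**5. Same mechanism in both arms.** With no true effect, the t-test bias is −0.009 to 0.004 and type I error 4.7% to 5.3%. With a true effect of 0.6 SD, the t-test understates it by 0.02 to 0.04 SD.

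**6. Random dropout.** The t-test's standard error should be near (SD of change) × √(2/(15(1 − dropout))): 0.272, 0.289, 0.322 and 0.342, which matches the simulation.

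| Set, dropout | SE, t-test | SE, repeated measures | Reduction |
|---|---|---|---|
| A, 10% | 0.272 | 0.254 | 6.6% |
| A, 20% | 0.291 | 0.267 | 8.2% |
| B, 10% | 0.321 | 0.294 | 8.4% |
| B, 20% | 0.342 | 0.303 | 11.4% |

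Repeat runs gave 6% to 10%. Most of the gain comes from the baseline score: in large samples √(1 − ρ²)/√(2(1 − ρ)) is 0.661/0.707 = 0.935 for A and 0.760/0.837 = 0.908 for B. The part beyond baseline adjustment is 2% to 4%.

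**7. Limits of the model.** Large-sample runs used mid–final change correlations of 0.5 to 0.9, 10% to 30% dropout and mechanisms that differ between arms. Where dropout depends on the observed mid score, the bias is 0.10 to 0.41 SD of change for the t-test and about 0 for the model. Where it depends on the unobserved final score, the bias is 0.20 to 0.46 for the t-test and 0.05 to 0.35 for the model. If the dropout in step 4 happens before the mid assessment, the model's bias is 0.045 to 0.102 baseline SD against 0.054 to 0.131 for the t-test.

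**The case against.** The strongest reply is that several tempting readings go beyond the text.

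- A reader might infer that the plan restricts Aim 1 to completers. It does not say so. The exclusion follows only from the absence of an imputation rule, and the text is visibly incomplete: section numbers jump from V to VII and the flow table is missing. A rule could sit in text not shown.
- A reader might infer that the primary comparison is biased. The documents give no dropout rate and no sign that dropout differs by arm. The trial is double-blind and sham-controlled, and under a common mechanism with no true effect the bias is about 0. Even in the one-arm scenario, 0.06 to 0.13 is well below the standard errors of 0.27 to 0.34, and a type I error of 5.6% is barely distinguishable from 5%.
- A reader might infer that a mid-study Jebsen Taylor score is collected and left unused. Visit 13, between the daily and weekly phases, fits a middle assessment, but only visit 22 is said to carry the full battery. If a mid score exists, the planned longitudinal model would use it.
- A reader might infer that the mixed model removes the problem. It does so only under missing at random, and not for patients lost before any post-baseline score.

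All four limits stand. What remains is that the leading test has no place for a patient without visit 22 unless values are imputed, and that the planned mixed model, as described, does not answer the Aim 1 question.

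**Conclusion.** The point holds as a conditional weakness in the choice of leading analysis, for Aim 1 and both Sub Aim 1.1 comparisons. The t-test can be biased if dropout is related to early response and differs between arms: about 0.06 to 0.13 baseline SD under 10% to 20% dropout in the active arm only, with type I error up to about 7%. Bias is not established, and under the null it is about 0 when both arms share the mechanism. The loss of precision does not need selective dropout: the repeated-measures standard error is about 7% to 10% smaller under random dropout, mostly through the baseline score. All sizes assume the stated correlations, normal scores and dropout model. The better analysis costs only wording, so the change is worth making, although the gap is not fatal.

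**What to change.** In the statistical text for the first aim, state that Aim 1 is decided by the group difference at visit 22 from a likelihood-based mixed model for repeated measures on all randomised patients, analysed as randomised, and use the same model for the two Sub Aim 1.1 contrasts. Specify group, visit and group-by-visit terms, an unstructured covariance and small-sample degrees of freedom. Enter the baseline Jebsen Taylor score as a response with its mean constrained equal across groups, so that patients with no post-baseline score also stay in the model.

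Use the mid-study score if the flow table confirms that it is collected. If it is not, the model offers little beyond a baseline-adjusted analysis. Keep the t-test as a supportive analysis and say how it treats missing values. Add one sensitivity analysis that shifts the missing visit 22 scores in the active arm by a stated amount.

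The cost is wording only: no new visit, patient or measurement. The downside is reliance on missing at random, which the shift analysis probes, and on approximate normality of timed scores, which is open to question because some patients will be unable to complete sub-tasks.

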• For sham rTMS stimulation, we will place the coil in the same location usually used for the active stimulation. We will also utilize the same stimulation parameters. However, we will replace the active coil with a sham coil to ensure no stimulation is actually provided.

Drug Intervention:

[figure not shown]
Fluoxetine:

- Subjects will receive fluoxetine 20 mg daily after enrollment during their baseline visit. They will take the study drug by mouth once daily from this day until the protocol is completed (for 90 days) we will use the same regimen as in the FLAME study.
- The drug will be dispensed by the pharmacy and nursing staff of Spaulding while subjects are inpatient at the hospital. Upon discharge from Spaulding subjects will be given the remaining pills in their prescribed amount supply and instructed to take one each day until finished.
- If the subject is discharged to a skilled nursing facility a copy of the protocol and contact information will be sent with the patient and the medication. Study staff will call the facility to answer questions and enlist support in continuing the study medication there. Study drug compliance will be monitored weekly via self-report measures either during a study visit or by phone. Subject's responses will be kept in a compliance log.
- If the subject is enrolled as outpatient a licensed physician on the study staff will dispense the medication to the subject during the baseline visit.

Placebo control:

• Subjects will receive a placebo pill daily after enrollment during their baseline visit. They will take the study drug by mouth once daily from this day until the protocol is completed (for 90 days). The placebo will be dispensed by the pharmacy and nursing staff of Spaulding while subjects are inpatient at the hospital. Upon discharge from Spaulding subjects will be given the remaining pills in their prescribed amount supply and instructed to take one each day until finished. The procedure for taking the study drug and to monitor for compliance will be the same as for the patients receiving the active drug.

www.randomization.com	

Clinical Assessments:

A rater blind to the treatment arm will administer the following:

- Jebson Taylor Hand Function Test (JTHF): This will be our primary outcome. This test
 was designed as a broad measure of hand function. It provides information on the time
 required for the subject to turn cards, pick up small objects, simulate feeding by picking up

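### The exploratory search for predictors of treatment effect names no comparator; if run within the combined arm alone, it finds predictors of outcome instead

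*Combined protocol and SAP*

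**What the plan says.** The analysis paragraph for the first aim plans a t-test between two groups on the Jebsen Taylor Hand Function test (JTHF), with covariate adjustment and mixed longitudinal models. It then adds an exploratory correlational analysis to learn "whether beneficial effects of the combined intervention (active rTMS and fluoxetine) are associated with any baseline characteristics as to explore potential predictors". The stated target is to "explore potential predictors of the effects of treatment". On later use, the plan says: "This result may also be used along with results for aim 2 to understand the mechanisms of the combined treatment".

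Four other places bear on this:

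- Aim 1 defines the effect of interest comparatively: whether the combination "offers an additional benefit on motor function over pharmacotherapy (fluoxetine) alone".
- Sub Aim 1.1 brings in the placebo arm "As to control for the effects of spontaneous recovery".
- Subject Selection says of eligibility: "We broadened the motor score criteria and time since stroke".
- The Study overview fixes the arm size: "15 patients will be randomized to each group".

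No baseline-by-arm interaction appears anywhere. Baseline variables serve only as adjustment covariates, and the one interaction in the plan is group by time, under the second aim.

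**The concern.** A treatment effect is a difference between arms, so a predictor of treatment effect is a variable whose relation to outcome differs between arms. The sentence names one intervention and a correlation. If that means correlating change with baseline inside the combined arm, the method does not estimate the stated target. A factor that forecasts recovery equally well under any treatment would be reported as predicting response to rTMS plus fluoxetine.

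Such factors are plausible here, because motor score and time since stroke were deliberately allowed to vary more widely. The plan accepts for mean outcomes that spontaneous recovery needs a control arm, but the predictor sentence mentions no such control. What is at stake is the hypothesis carried forward: a merely prognostic factor could enter the account of how the combined treatment works.

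**Working it through.** **Inputs.** From the documents: three arms of 15, and 3 × 15 = 45 agrees with the stated total. The documents give no significance level, JTHF standard deviation, correlation or list of baseline variables. Two-sided 0.05 and all correlations below are therefore assumptions, used for illustration only.

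**Step 1: what each analysis estimates.** Let x be a baseline variable. In the combined arm, the slope of change on x is (prognostic slope) + (slope of the treatment effect on x). In the comparator arm, it is the prognostic slope, plus any modification of the fluoxetine effect if the comparator is fluoxetine plus sham rTMS. Only the difference between the two slopes isolates modification of the added rTMS effect. A one-arm correlation returns the sum.

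**Step 2: significance threshold in one arm.** With n = 15 there are 13 degrees of freedom and t = 2.160. The critical correlation is t/√(13 + t²) = 2.160/√(13 + 4.667) = 0.514.

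**Step 3: a purely prognostic factor.** Simulated normal data, 15 per arm, the same correlation with change in both arms, so no effect modification. The interaction test compares the two slopes on 26 degrees of freedom.

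| Correlation with change | Flagged, one arm | Flagged, interaction |
|---|---|---|
| 0.2 | about 11% | about 5% |
| 0.3 | about 19% | about 5% |
| 0.4 | about 32% | about 5% |
| 0.5 | about 50% | about 5% |

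The one-arm figures are power to detect a real association with outcome. They become errors only when the result is reported as effect modification.

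**Step 4: the reverse error.** Take a true modifier with correlation 0 in the combined arm and −0.5 or −0.7 in the comparator. The one-arm test flags it in 5% of trials; the interaction test in 26% or 50%.

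**Step 5: power of the interaction.** With correlation 0.5, 0.6 or 0.7 in the combined arm and 0 in the comparator, power is 26%, 37% or 50%.

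**Step 6: scale, if baseline JTHF is itself tested.** The primary outcome "was designed as a broad measure of hand function. It provides information on the time" needed for a series of hand tasks, so skewed values are plausible. Assume log-normal times with log-SD 0.3 to 0.8, baseline to follow-up correlation 0.7 to 0.9 on the log scale, and no treatment effect. The baseline-by-arm test on raw change then rejects in about 8–28% of trials, and on the log scale in about 5%.

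**The case against.** The best defence is that a comparative analysis was meant. The sentence sits in the Aim 1 paragraph, shortly after the two-group comparison and covariate adjustment, and Aim 1 defines benefit relative to fluoxetine alone. This stands to the extent that the one-arm analysis is an inference. A reader might conclude that the plan definitely correlates within one arm; the text does not say so. What is established is that the comparator and interaction are missing from the wording. Even on the comparative reading they need to be stated.

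It can also be said that the analysis is openly exploratory, with no multiplicity correction claimed, and that mechanism is addressed mainly through the Aim 2 model. This limits the weight of the point. It does not remove it, because the exploratory label says how strong the evidence is, not which quantity is estimated.

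A third objection is that the interaction is underpowered and depends on scale. Both are true. Low power calls for cautious reporting, not for testing a different quantity. On scale, a reader might infer that every significant raw-scale interaction with baseline JTHF is a false positive. That goes too far. Suppose treatment cuts every follow-up time by 20%. The slope of raw change on baseline then truly differs between arms by −0.2 × b, where b is the slope of follow-up on baseline. Under the Step 6 assumptions, b = (exp(s²ρ) − 1)/(exp(s²) − 1), with s the log-SD and ρ the log-scale correlation. For s = 0.8, ρ = 0.7, b is 0.63 and the difference −0.13. For s = 0.3, ρ = 0.9, b is 0.90 and the difference −0.18. Rejections in that setting reflect scale dependence. Only the no-effect figures of 8–28% measure error.

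**Conclusion.** The point holds, conditionally and at low severity. The plan seeks predictors of treatment effect without naming a comparator or an interaction. On the one-arm reading the method answers a different question, and a purely prognostic factor of modest strength (correlation 0.2 to 0.5) would be flagged in roughly one trial in nine to one in two, against about one in twenty for an interaction test. These rates rest on normal data, two-sided 0.05 and correlations that the documents do not supply.

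A reader might infer that the trial's main conclusions are weakened. The documents do not support that: the primary JTHF comparison, the two Sub Aim 1.1 comparisons and the Aim 2 tests do not use this analysis. The only route to harm is the stated possible use in interpreting mechanism.

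**What to change.** Choose one of two wordings before unblinding.

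**(a) Relabel.** If the one-arm correlation is kept, call its results predictors of outcome in the treated arm, show the same correlations in all three arms side by side, and do not use them as evidence on mechanism. This costs a few sentences.

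**(b) Change the estimand.** If a claim about predictors of treatment effect is wanted, base it on an exploratory baseline-by-arm interaction:

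- Make fluoxetine plus active rTMS against fluoxetine plus sham rTMS the main contrast.
- Name a few baseline variables before unblinding.
- State the outcome scale in advance. If baseline JTHF is among the variables, note that the result depends on that scale.
- Report estimates with 95% confidence intervals as hypothesis-generating.

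This costs one extra model per listed variable, with no new arm or visit. The downside is that with 15 per arm power is low (26–50% even for the strong modifiers in Step 5) and intervals are wide, so real modifiers may be missed. A modifier on the log scale also need not be one in seconds.
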